12.1.4 Definitions for Statistical Data Analysis

The following definitions (Table 21) for statistical analyses/presentations will be used:

Table 21: Definition of Terms for the Statistical Analysis

Term	Definition
Baseline Value	The last subject's assessment prior to subject's first randomized product use in mCC / THS 2.2 Menthol arms. In the SA arm, the subject's last assessment prior to 10:00

AM on Day 1

Where the baseline is different for any of the variables measured this will be specified in the relevant section.

In this SAP, references to the Day 30 Visit, Day 60 Visit and Day 90 Visit, Day 30, Day 60, and Day 90 refer to the nominal days.

Nominal Day 31 will be referred to as the second day of the Day 30 Visit. Nominal Day 61 will be referred to as the second day of the Day 60 Visit. Nominal Day 91 will be referred to as the second day of the Day 90 Visit.

For urine collections taken on Days x to y, e.g., Days 5 to 6, these will be referred to as collected on Day x, e.g., Day 5, in the SAP.

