7.5.1 Biomarker of Exposure

7.5.1.1 Exhaled CO and Carboxyhemoglobin

Carboxyhemoglobin measured in blood and exhaled CO will be investigated as a measure of exposure to CO in all three study arms. A CO breath test should be conducted in timely conjunction with the blood sampling for COHb, where applicable. In the SA arm, the CO breath test will serve as a verification of compliance. (Section 6.5.4).

CO Breath Test

Carbon monoxide in exhaled breath will be measured using the Smokerlyzer® device such as Micro 4 Smokerlyzer® device or similar in all 3 study arms.

During the confinement period on Days -1 to Day 5, the CO breath test will be conducted four times per day. The first assessment should be conducted within 15 minutes prior to the first product use. The other 3 assessments should be conducted as described in Section 9.

For subjects in the SA arm from Day 1 onwards, the first CO breath test will be done at between 08:00 AM-09:30 AM. The other 3 assessments should be conducted as described in Section 9.

On Day -2 and Day 6, and during the ambulatory period on Day 30 Visit (Day 30), Day 60 Visit (Day 60), and Day 90 Visit (Day 90), the CO breath tests will be conducted once, irrespective of time of product use.

Carboxyhemoglobin

COHb measurement will be performed in all 3 study arms at a local laboratory. Carboxyhemoglobin will be assessed on a daily basis from Day-1 until Day 5.

On Day -1 to Day 4: one blood sample will be collected in the evening between 8:00 PM-09:30 PM.

On Day 5: one blood sample will be collected within 15 minutes prior first product use. The three other blood samples will be collected as described in Section 9.

For subjects in the SA arm from Day 1 onwards, the first COHb will be done between 08:00AM-09:30 AM. The three other blood samples will be collected as described in Section 9.

On Day 30 Visit (Day 30), Day 60 Visit (Day 60) and Day 90 Visit (Day 90): for all study arms, one blood sample will be collected during the visit, irrespective of the time of product use.

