7.5.1.3 Other Biomarkers of Exposure

BoExp will be measured as per the Schedule of Events (see Appendix 1):

- in 24-hour urine collection samples during the confinement period from Day -1 onwards to Day 5.
- in 24-hour urine collection during the ambulatory period collected on Day 30 Visit, on Day 60 Visit, and on Day 90 Visit.

The following BoExps will be measured:

- Selected primary BoExp: MHBMA, 3-HPMA, S-PMA, and total NNAL
- Selected secondary BoExp: Total 1-OHP, total NNN, 4-ABP, 1-NA, 2-NA, o-tol, NEQ, CEMA, 3-hydroxybenzo(a)pyrene, HEMA, S-BMA and HMPMA.

For normalization of BoExp, creatinine will also be measured in the 24 hour urine samples.

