7.8.2 Human Smoking Topography Assessment

Human smoking topography (HST) involves the measurement of each smoker's unique way of smoking mCCs or using Menthol Tobacco Sticks using the HST SODIM® device. The HST SODIM® device, model SPA/M (SODIM® Instrumentation, Fleury les Aubrais, France) is a device which is used to measure smoking topography (see Appendix 5). It consists of a special sample holder (containing a constriction in the middle) which is placed between the smoker's mouth and the filter of the mCC or menthol THS Tobacco Stick being smoked/used. The holder is connected by two narrow tubes to a portable data logger/recording system (see Appendix 5) for a description of the device.

At Day 0, the HST SODIM® device has to be used for all mCC smoked for all subjects. On Day 1 and Day 4 of the confinement period the HST SODIM® device has to be used for every smoking event for all subjects in the mCC and THS 2.2 Menthol arms. On Day 30 Visit (Day 30), Day 60 Visit (Day 60), and Day 90 Visit (Day 90) of the ambulatory period, HST SODIM® device will start between 08:30 and 09:30 AM with 4 hours recording. Smoking topography with the HST SODIM® device will **not** be done in subjects smoking mCC that are incompatible with the HST SODIM® device (e.g. slim mCC). For subjects in the SA arm, no HST assessments will be performed.

For each subject, one HST SODIM® device will be assigned at Day -1, which will be used by that subject on all HST assessment days (in the case of malfunction, the device will be exchanged). HST SODIM® devices will be assigned to all subjects smoking non-slim mCCs.

The Sponsor will provide training on the use of the HST SODIM® device to the study collaborators. The study collaborators will, in turn, provide training to the subjects. All HST SODIM® devices will be returned to the sponsor after completion of the study.

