**Table 10. Time Schedule – Day 0**

Time	Blood sample	Procedures	Additional information
Start of procedure	Baseline Day 0		
		AE/SAE questioning; Concomitant medication	All Day
		Randomization	At any time of the day after eligibility criteria have been met. Subjects are not to be informed of their assigned arm until Day 1
06:29 AM+/-20min		End of 24-hour urine collection and samples to be taken from the 24-hour urine after the final portion of urine has been added to Day -1 sampling bottle.	BoExps (primary secondary and NEQ) and creatinine
06:30 AM+/-20min		Start collection of 24-hour urine to Day 0 sampling bottle	
	√	CYP2A6 activity in plasma	Has to be done prior to smoking
		Spirometry without short-acting bronchodilator	Has to be done prior to smoking
		Assessment of cough	Has to be done prior to smoking but no later than 10:00 AM
		MNWS questionnaire	Has to be done prior to smoking but no later than 10:00 AM
		CO breath test	Within 15 minutes before first smoking event.
06:30 AM to 11:00 PM		HST	HST SODIM® device has to be done for all product uses if compatible mCCs are smoked
06:30 AM		Beginning of smoking	
	√	Clinical laboratory parameters (hematology, clinical chemistry) and risk markers: hs-CRP, fibrinogen, homocysteine, LDL, HDL, HbA1c, sICAM-1	Has to be done after at least 10 hours of fasting. Blood glucose, TG, TC, WBC, platelet count from safety will be evaluated also as risk markers

Data and information contained in this document are considered to constitute trade secrets and confidential commercial information, and the legal protections provided to such trade secrets and confidential information are hereby claimed under the provisions of applicable law. No part of this document may be publicly disclosed without the written consent of Philip Morris Products S.A.

Time	Blood sample	Procedures	Additional information
Start of procedure	Baseline Day 0		
	√	Blood sampling for bio-banking for transcriptomics	If consent is obtained Has to be done after at least 10 hours of fasting
	√	Bio-banking for BoExp/ risk markers in serum/plasma (if consent is obtained)	If consent is obtained Has to be done after at least 10 hours of fasting
Before 10:00 AM		Urine safety analysis	
Before 11:30 AM		Breakfast	
10:00 AM-11:30 AM		Vital signs (blood pressure, pulse rate, respiratory rate)	At least 5 minutes in supine position prior to measurement Systolic and diastolic BP to be evaluated also as risk markers

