12.1.2 Definitions for Statistical Data Analysis

Baseline:

In general, baseline will be the last available time-point prior to Day 1, 06:30 AM.

THS 2.2 Menthol users: Subjects switching from mCC to THS 2.2 Menthol whose product use pattern categorization is primarily THS 2.2 Menthol or predominantly THS 2.2 Menthol over a defined period will be considered as THS 2.2 Menthol users during that period.. See Section 12.3 for further details on the product use.

Dual use:

Subjects switching from mCC to THS 2.2 Menthol whose product use pattern categorization is dual mostly THS 2.2 Menthol, dual balanced or dual mostly CC over a defined period will be considered as dual users. See Section 12.3 for further details on the product use.

CC users:

Subjects switching from mCC to THS 2.2 Menthol or subjects continuing to use mCC whose product use pattern categorization is primarily CC or predominantly CC over a defined period will be considered as CC users during that period. See Section 12.3 for further details on the product use.

Smoking abstinence:

Data and information contained in this document are considered to constitute trade secrets and confidential commercial information, and the legal protections provided to such trade secrets and confidential information are hereby claimed under the provisions of applicable law. No part of this document may be publicly disclosed without the written consent of Philip Morris Products S.A.

Smoking abstinence during a defined period is defined as using no tobacco-containing product as reported by the subject on the electronic diary.

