12.6.1 Primary Analyses

12.6.1.1 Analysis of Biomarkers of Exposure for Primary Objectives

The BoExp (COHb in blood and urinary concentrations of MHBMA, 3-HPMA, S-PMA and Total NNAL) used for the primary analysis will be described as detailed in Section 12.1.3 “Descriptive Statistics”. The listing of the COHb data will have a flag for whether a subject’s COHb was <2%.

The baseline is as defined in Section 12.1.4 “Definitions for Statistical Data Analysis”.

The primary endpoints will be log-transformed (base_e) prior to analysis. The analysis will compare the evening COHb level (20:00-21:30) at Day 5; and urinary concentrations of MHBMA, 3-HPMA and S-PMA adjusted for creatinine on Day 5 and urinary concentrations of Total NNAL adjusted for creatinine on Day 90 Visit between the THS 2.2 Menthol and mCC arms for the PP Set. An analysis of covariance (ANCOVA) (Snedecor and Cochran 1982) model will be used with terms for the log-transformed baseline value, sex, average daily mCC consumption over the last 4 weeks as reported during screening and randomization arm.

The SAS code to be used for the THS 2.2 Menthol and mCC data is shown below:

```
Proc glm data=_data_ ;
  Class randomization_arm sex cigarette_cons;
  Model log_biomarker = log_baseline sex cigarette_cons
    randomization_arm;
  Lsmean randomization_arm / pdiff =control('mCC') alpha=0.05 cl;
  Run;
```

The least squares (LS) means and estimate of the difference and the 95% CI will be back-transformed. The geometric LS means for each randomization arm along with the ratio (THS 2.2 Menthol : mCC), two-sided 95% CI and one-sided p-value will be presented in the tables. THS 2.2 Menthol : CC effects will be graphed in a forest plot.

All figures, summaries and analyses will be performed on the PP Set. Additional descriptive statistics will be provided within the secondary analysis.

The data will be presented in the below outputs:

TFL number	Title
FIGURES	
15.1.1.1	Forest Plots of Statistical Analysis of Biomarkers of Exposure for Primary Objective – PP Set
15.1.1.2	Biomarker of Exposure for Primary Objective Arithmetic Mean and 95% CI for Percent Change from Baseline – PP Set
TABLES	
15.2.3.1.1	Analysis of COHb, MHBMA, 3-HPMA, S-PMA and Total NNAL on Day 5/90 Visit for THS 2.2 Menthol versus mCC for the Primary Objective – PP Set
15.2.4.1.1	Descriptive Statistics of Blood COHb (%) – PP Set
15.2.4.1.1.1	Descriptive Statistics of Blood COHb (%) by Sex – PP Set

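### The primary ANCOVA adjusts only for the Day 0 value, although Day -1 is also measured for all five primary biomarkers: a possible, modest loss of precision

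*SAP*

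**What the plan says.** **Baseline rule.** SAP 12.1.4 (Table 21) takes "The last subject's assessment prior to subject's first randomized product use in mCC / THS 2.2 Menthol arms". Protocol 12.1.2 has the same kind of rule: "In general, baseline will be the last available time-point prior to Day 1, 06:30 AM". SAP 12.6.1.1 makes no exception for the primary biomarkers ("The baseline is as defined in Section 12.1.4"), and its model has a single baseline term: "Model log_biomarker = log_baseline sex cigarette_cons", plus randomization arm.

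**What is measured before randomized product use.** Protocol 7.5.1.3 plans the urinary biomarkers, including MHBMA, 3-HPMA, S-PMA and total NNAL, "in 24-hour urine collection samples during the confinement period from Day -1 onwards to Day 5". Protocol Table 10 lists "BoExps (primary secondary and NEQ) and creatinine" for the Day -1 collection, and Table 11 lists the same for the Day 0 collection. For COHb, Protocol 7.5.1.1 says "On Day -1 to Day 4: one blood sample will be collected in the evening between 8:00 PM-09:30 PM". SAP 12.6.1.1 analyses the Day 5 COHb sample from that same evening window. SAP Table 18 gives the Day -1 and Day 0 samples identical time windows.

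**Topography device.** Protocol 7.8.2 states "At Day 0, the HST SODIM® device has to be used for all mCC smoked for all subjects", and the same section exempts incompatible cigarettes such as slim ones. The other full device days in confinement are Days 1 and 4; the Day 30, 60 and 90 Visits have a four-hour recording. No device use is scheduled on Day -1 or Day 5. Protocol 7.8.3.6 adds an exploratory questionnaire on whether the device disrupts smoking.

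Neither document explains why Day -1 is left out of the covariate, and no sensitivity analysis uses it.

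**The concern.** An ANCOVA gains precision in proportion to how well the baseline covariate predicts the outcome. One day's value of a biomarker with a half-life of about a day or less carries day-to-day variation. A second assayed value can reduce that variation, and here it already exists.

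The day that is kept also differs from the Day 5 outcome day: cigarettes are smoked through the device by subjects with compatible brands and without it by the others. If the device changes intake by different amounts in different subjects, Day 0 predicts Day 5 less well.

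At stake is the width of the confidence interval for the THS 2.2 Menthol to mCC ratio. Percent change from Day 0 is also summarised, but only descriptively.

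**Working it through.** **1. The plan's own power.** The inputs are the mean ratios (MR) and CVs in SAP Tables 11 to 13, 80:40 subjects on Day 5 and 40:40 for total NNAL (SAP Table 14), a 50% margin and one-sided alpha of 2.5%. On the log scale, delta = ln(0.50/MR) and SD = sqrt(ln(1+CV²)).

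- COHb, YVD-CS01-EU: delta = ln(0.50/0.40) = 0.223; SD = sqrt(ln(1+0.32²)) = 0.312; SE = 0.312 × sqrt(1/40+1/80) = 0.0605; power 95.8%.
- Total NNAL: delta = ln(0.50/0.30) = 0.511; SD = 0.555; SE = 0.555 × sqrt(2/40) = 0.124; power 98.5%.
- The other three are at 99.99% or above.

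The product of the five, assuming independence, is 94.3%; with the ZRHX-EX-01 inputs it is 98.2%. The 94% and 98% in SAP Table 15 reproduce. No baseline correlation enters that calculation.

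**2. One baseline day against two.** Let rho be the correlation of each baseline day with the outcome, and r the correlation between Day -1 and Day 0. Relative to the unadjusted variance, the residual variance is:

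- one day: 1 − rho²
- mean of two days: 1 − 2rho²/(1 + r)

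If both days predict equally well, entering them as two covariates gives the same value as the mean. The documents give neither rho nor r, so every value below is assumed.

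| rho | r | one day | two days | variance ratio | CI width ratio |
|---|---|---|---|---|---|
| 0.3 | 0.95 | 0.910 | 0.908 | 0.997 | 0.999 |
| 0.5 | 0.5 | 0.750 | 0.667 | 0.889 | 0.943 |
| 0.7 | 0.95 | 0.510 | 0.497 | 0.975 | 0.988 |
| 0.7 | 0.9 | 0.510 | 0.484 | 0.949 | 0.974 |
| 0.7 | 0.7 | 0.510 | 0.424 | 0.830 | 0.911 |
| 0.9 | 0.9 | 0.190 | 0.147 | 0.776 | 0.881 |

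Residual variance falls by 0.3% to 22%, and the interval narrows by about 0 to 12%. The larger gains need adjacent days to correlate no better with each other than with an outcome five or more days later. Adjacent days will often correlate more closely, which moves the gain toward the low end.

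**3. Effect on power.** Suppose the stated CVs already describe the spread left after adjustment for one baseline, and apply the same variance ratio to all five biomarkers. Overall power at the 50% margin then moves from 94.3% to between 94.4% and 98.4% (YVD-CS01-EU), and from 98.2% to between 98.2% and 99.6% (ZRHX-EX-01).

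**4. If Day -1 predicts less well.** For unequal correlations a (Day 0) and b (Day -1) with the outcome, the mean explains (a+b)²/(2(1+r)), and two separate terms explain (a²+b²−2abr)/(1−r²). Assumed cases:

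- a = 0.70, b = 0.65, r = 0.90. Day 0 alone explains 0.490. The mean explains 1.35²/3.8 = 0.480, so residual variance is 0.520/0.510, 2% higher. Two terms explain 0.0935/0.19 = 0.492, slightly better than Day 0 alone.
- a = 0.70, b = 0.60, r = 0.85. The mean explains 1.30²/3.7 = 0.457, so residual variance is about 6.5% higher. Two terms explain 0.136/0.2775 = 0.490, no loss.

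**5. Price of the extra term.** The two-arm model has five parameters, so residual degrees of freedom go from 120 − 5 = 115 to 114 on Day 5, and from 80 − 5 = 75 to 74 for total NNAL.

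**The case against.** The protocol and SAP agree on a conventional rule, so this is not an error.

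Day 0 is not shown to be the worse day. No effect of the device on intake or biomarkers is reported; the questionnaire only asks about it. A proportional shift common to all subjects would be a constant on the log scale and would leave the contrast unchanged. Only effects that differ between subjects would hurt.

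Day -1 has its own peculiarities. It is the first full day in confinement and on a single brand (Protocol 5.1), and it follows the Day -2 product test of up to three sticks. Day 5 follows a full device day, and the Day 90 Visit includes four device hours, so the contrast between device and device-free days is not clean. With its 10 to 15 day half-life (Protocol 4.2), total NNAL should hardly differ between adjacent days.

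All of this stands. It limits the size of the gain and favours using both days over replacing Day 0 with Day -1. It does not supply a reason to discard a value already assayed. The case in which a simple mean loses is avoided by entering the two days as separate terms.

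A reader might infer that the device day biases the comparison of THS 2.2 Menthol with mCC. The documents do not support that: Day 0 precedes disclosure of the arm, and the device applies to all subjects alike on that day, subject only to cigarette compatibility.

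**Conclusion.** The point holds as a possible loss of precision. The primary ANCOVA uses one of two comparable pre-product values, and the one used comes from a device day for most or all subjects, depending on how many smoke incompatible cigarettes (a number not given).

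Under assumed correlations the interval narrows by about 0 to 12%. That range treats both days as equally predictive and must be read against the pooled residual variance of the two arms, since the planned model has one common residual variance and slope. The gain is most plausible for COHb and the short half-life mercapturic acids and may be nil for total NNAL.

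A reader might also infer that the study is underpowered. It is not shown to be: the 94% and 98% at the 50% margin reproduce without any baseline correlation, and trial success is unlikely to turn on this choice. The matter is a cheap improvement.

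**What to change.** In SAP 12.6.1.1, before database lock, specify that for the primary biomarkers both the log Day -1 and log Day 0 values enter the ANCOVA as covariates. Alternatively, use the mean of the two logs, with the single available value if one is missing. If the two-term version is chosen, state how a subject with one missing day is kept in, because SAP 12.1.5 does not impute missing baselines and PROC GLM would drop that subject.

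SAP 12.1.4 already allows a different baseline to be set in the section concerned, and SAP 12.6.2.2 does so for nicotine and cotinine. List the change in SAP Section 9, because it departs from Protocol 12.1.2, and say whether the analyses that reuse the primary model (SAP 12.6.1.3, 12.6.2 and 12.6.2.1) follow it.

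No new samples or assays are needed. The costs are one model degree of freedom and, if the simple mean is chosen, a possible small loss should Day -1 predict less well than Day 0.

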Before 06:30 AM		Subjects are informed of their assigned study arm		
06:29 AM+-20min		End of 24-hour urine collection and samples to be taken from the 24-hour urine after final portion of urine has been added to Day 0 sampling bottle.	BoExps (primary, secondary and NEQ), creatinine, and Ames mutagenicity in 24-hour urine Risk markers: 11-DTX-B2, 8-epi-PGF2 α , Bio-banking for BoExp/ risk markers (if additional consent is obtained)	

Data and information contained in this document are considered to constitute trade secrets and confidential commercial information, and the legal protections provided to such trade secrets and confidential information are hereby claimed under the provisions of applicable law. No part of this document may be publicly disclosed without the written consent of Philip Morris Products S.A.

Time	Blood sample	Procedures	Additional information
Start of procedure		Day 1	
06:30 AM+/-20min		Start collection to Day 1 sampling bottle 24-hour urine Assessment of cough (VAS) MNWS questionnaire CO breath test	Must be prior to first product use of Day 1 To be done prior to product use but no later than 10:00 PM To be done prior to product use but no later than 10:00 PM Within 15 minutes before first product use (for THS 2.2 Menthol and mCC arms) or between 08:00 AM-09:30 AM (SA arm)
06:30 AM-11:00 PM		HST	In THS 2.2 Menthol and mCC arms, it should be done for all smoking events with HST SODIM® device, if compatible mCCs are smoked
06:30 AM		Beginning of product use	
Before 10:00 AM		Breakfast	
10:00 AM-11:30 AM		Vital signs (blood pressure, pulse rate, respiratory rate)	At least 5 minutes in supine position prior to measurement
12:00 PM-01:30 PM		CO breath test	
Before 02:30 PM		Lunch	
04:00 PM-05:30 PM		CO breath test	
Afternoon		Snacks	
In the evening before 09:00 PM		Dinner	
08:00 PM-09:30 PM		CO breath test	
08:00 PM-09:30 PM	✓	COHb in blood	
08:00 PM-09:30 PM	✓	Nicotine, cotinine in plasma	
08:00PM-11:00 PM		MCEQ questionnaire (THS 2.2 Menthol and mCC arms only), QSU-brief questionnaire	
11:00 PM		End of product use	
6:30 AM-11:15 PM		Collection of used mCC butts	For accountability

Time	Blood sample	Procedures	Additional information	
Start of procedure		Day 1		
6:30 AM-11:15 PM		Collection of all tobacco plugs and filters from Menthol Tobacco Sticks	For accountability and further analysis	

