**Table 1 Definition of Study Arms**

Study arm	Number of subjects
THS 2.2 Menthol	80
mCC	40
Smoking abstinence	40

However, one of the sites was closed down after a good clinical practice failure, and 160 subjects were randomized at the Tokyo Heart Centre site along with those subjects randomized at the Seisukai site prior to the site being shut down.

This is an *ad libitum* smoking study. In general, smoking/product use during the confinement period will be allowed between 06:30 AM and 11:00 PM. During the ambulatory period, there will be no smoking/product use restriction except during the three visits on site (Day 30 Visit, Day 60 Visit, and Day 90 Visit), when product use will be allowed from 08:00 AM to around 23:00 PM on Day 30, Day 60, and Day 90. Smoking/product use before 08:00 AM on Day 30, Day 60 and Day 90 are not restricted. During the second day of the Day 30 and Day 60 Visits, product use will be allowed from 06:30 AM onwards. On the second day of the Day 90 Visit, product use will be allowed after the CYP2A6 activity, MNWS and cough questionnaires and spirometry have been performed until time of discharge.

The Screening Visit will be conducted within 4 weeks prior to Admission to the investigational site (Day -30 to Day -3). Screening procedures do not necessarily have to be conducted on the same day. During the Screening Visit the study collaborator will demonstrate the use of THS 2.2 Menthol.

Prior to enrollment on Day -2, as the last procedure of the eligibility assessments, subjects will have a product test of the THS 2.2 Menthol (use of up to 3 THS Menthol Tobacco Sticks). In female subjects, the THS 2.2 Menthol product test will only be done after pregnancy is excluded by a negative urine pregnancy test. Enrollment takes place after all inclusion and exclusion criteria have been satisfactorily met. Only subjects willing and able to use the product will be enrolled in the study.

Subjects are admitted and enrolled on Day -2, but not randomized until Day 0. From Day -2 to Day 0, all subjects continue smoking their single preferred brand of mCC and baseline values will be recorded. On Day 0, subjects will be randomized to one of the 3 study arms (Table 1). Subjects will be informed of their product allocation by the study site staff on Day 1 prior to 06:30 AM.

The exposure period (from Day 1 06:30 AM until time of Discharge on Day 91) will include both the exposure in confinement and the exposure in the ambulatory setting.

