12.1.3 Descriptive Statistics

For continuous data, summary statistics will include the number of subjects (n), the number and percent of subjects with missing data, the arithmetic mean, arithmetic standard deviation (SD), 95% confidence interval (95% CI), median, first and third quartiles, minimum and maximum; for log-normal data the geometric mean, geometric 95% confidence interval and geometric coefficient of variation (CV) will also be presented instead of the SD and 95% CI of the arithmetic mean. For categorical data, frequency counts and percentages will be presented. Data listings will include all subject level data collected unless otherwise specified.

Unless otherwise specified, data described over time will be reported for the 2 – 4 periods (see Table 20).

Data for early termination will be summarized at the end of the corresponding period (1-4). Data for early termination collected during an unplanned ambulatory visit will be handled as specified in Section 12.1.6 “Handling of Unplanned Data”.

Urinary BoExp Summaries

In general, urinary BoExp will be described over time as follows:

- Summary of concentration values adjusted for creatinine, and their percent change from baseline. Line graphs will be produced for arithmetic means of creatinine adjusted concentration (and 95% CI of the mean) for the percent change from baseline over all timepoints.
- Summary of quantity excreted over 24-hours values.

In general, BoExp measured in blood or breath tests will be described with summaries of the levels over time and levels expressed as percent change from baseline. BoExp levels will also be presented with line graphs.

Summaries and graphs will be produced for the FAS and PP Set. All derived variables will be listed together with the raw BoExp levels.

Safety Summaries

In general, summaries for the Safety and Full Safety populations will be produced by randomization arm, separately for the following periods:

- Pre-Randomization, including safety data collected until randomization. Only for this period, the Safety population includes any subjects who tested the product but were not randomized and these subjects will be reported in a separate “Product Test Only” group.
- Randomized period, including Baseline and all post-Baseline data.

The following product labels will be used throughout the TFLs (Table 19):

Table 19: Product Labels

Product	Format used in TFLs	Order in TFLs
Tobacco Heating System 2.2 Menthol	THSm2.2	1

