12.6.2.2 Nicotine and Cotinine Concentrations

The concentrations of nicotine and cotinine will be listed and summarized. During confinement, the evening concentration levels at 08:00 PM is considered. Baseline is the assessment at 08:00 PM to 09:30 PM on Day 0. Line graphs of the nicotine and cotinine concentration profiles across all study days showing mean and 95% CI of percent change from baseline will also be produced.

Nicotine and cotinine concentrations at each post-baseline timepoint will be analysed in the log space using an ANCOVA model with terms for log-transformed baseline concentration, sex, average daily mCC consumption over the last 4 weeks as reported during screening, time point, product, and the interaction term between time point and product. No adjustment will be made for multiple comparisons.

The SAS code described in Section 12.6.1.3 "Sensitivity Analysis" will be used for the analysis of nicotine and cotinine.

Geometric LS means for each product along with the ratio (THS 2.2 Menthol : mCC) and 95% CI will be presented in the tables.

All figures, summaries and analyses will be performed on the PP Set and FAS by randomization arm.

The data will be presented in the below outputs:

TFL number	Title
FIGURES	
15.1.2.1.1	Plasma Nicotine and Cotinine Profile (ng/mL) over the 90 Days Arithmetic Mean and 95% CI for Percent change from baseline – PP Set

TFL number	Title
15.1.2.1.2	Plasma Nicotine and Cotinine Profile (ng/mL) over the 90 Days Arithmetic Mean and 95% CI for Percent change from baseline – FAS
TABLES	
15.2.4.19.1	Descriptive Statistics of Plasma Nicotine and Cotinine Concentrations (ng/mL) – PP Set
15.2.4.19.2	Descriptive Statistics of Plasma Nicotine and Cotinine Concentrations (ng/mL) – FAS
15.2.4.20.1	Analysis of Plasma Nicotine and Cotinine Concentrations (ng/mL) over the 90 Days – PP Set
15.2.4.20.2	Analysis of Plasma Nicotine and Cotinine Concentrations (ng/mL) over the 90 Days – FAS
LISTINGS	
15.3.3.3	Listing of Plasma Nicotine and Cotinine Concentrations

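### The exhaled-CO baseline is a Day 1 morning reading, taken in the SA arm after abstinence has begun; this biases the THS-versus-SA contrast and understates percent reductions at later times of day

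*SAP*

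**What the plan says.** SAP Section 12.1.4 (Table 21) defines baseline as the last assessment before the "first randomized product use in mCC / THS 2.2 Menthol arms". For the third arm the text is "In the SA arm, the subject's last assessment prior to 10:00" AM on Day 1. It adds: "Where the baseline is different for any of the variables measured this will be specified in the relevant section".

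Protocol Section 9.2.3 (Table 11, Day 1) times the first CO breath test as "Within 15 minutes before first product use (for THS 2.2 Menthol and mCC arms) or between 08:00 AM-09:30 AM (SA arm"). SAP Table 18 repeats these windows. SAP Section 6.1 states that "smoking/product use during the confinement period will be allowed between 06:30 AM and 11:00 PM".

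Protocol Section 12.1.2 has a different rule: "In general, baseline will be the last available time-point prior to Day 1, 06:30 AM". Protocol Section 6.2.3.3 starts abstinence at 06:30 AM on Day 1, and the SAP's own list of special terms ends the baseline period at 06:29 AM that day. The SAP revision history mentions the 10:00 AM reference for SA, but SAP Section 9 (changes from the protocol) does not list it.

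SAP Section 12.6.2.1, which covers exhaled CO, sets no separate baseline. Section 12.6.2.2 does so for nicotine and cotinine: "Baseline is the assessment at 08:00 PM to 09:30 PM on Day 0". Under SAP Section 12.1.3, breath-test markers are described by "summaries of the levels over time and levels expressed as percent change from baseline". Under Section 12.6.2.1, CO is analysed untransformed with the baseline-adjusted model and compared with both mCC and SA.

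**The concern.** CO is tested four times a day in confinement, so a rule that picks the last test before a cut-off also picks a time of day. Here it picks the morning, after the overnight ban on smoking. Later readings taken during permitted product use are then compared with a low starting value, and overnight washout is mixed with the product effect.

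In SA the chosen reading is later still and falls after the intervention has started. SAP Section 12.4 itself declines to use SA CO as a compliance check before Day 2 because of possible carry-over, so it treats Day 1 as a transition.

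At stake is one secondary endpoint. The protocol uses SA as the reference point for the greatest achievable reduction, so an error that narrows the THS-SA gap favours the test product.

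**Working it through.** **The plan's own figures.** The plan gives no figure for the CO baseline and no expected ratio for exhaled CO. The nearest is the COHb row of SAP Table 11: THS/CC 0.40 and THS/SA 2.10. The 0.40 feeds the 94% joint power in SAP Table 15. With σ = √ln(1+CV²), power per endpoint is Φ[ln(0.5/MR)/(σ√(1/n₁+1/n₂)) − 1.96]. Multiplied over the five endpoints at the SAP Table 14 sizes, this gives 0.943, which agrees. That figure is not in dispute.

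**Smoke-free time at baseline.** From 11:00 PM to 06:30 AM is 7.5 hours, the minimum for a THS or mCC subject who starts at 06:30. To 08:00-09:30 AM it is 9 to 10.5 hours (SA), which is 1.5 to 3 hours after abstinence starts.

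**Percent change shown for an evening reading.** Let r be the baseline divided by the usual evening level. The displayed change is 0.40/r − 1 for a THS subject (true −60%) and 1/r − 1 for an unchanged mCC smoker (true 0%). The documents give no CO half-life T; the protocol states only 24 hours or less for the Day 5 primary markers as a group. Two washout models are shown over h = 7.5 hours:
- decay to zero: r = 2^(−h/T);
- decay to a floor: r = f + (1 − f)·2^(−h/T), with f = SA/mCC = 0.40/2.10 = 0.190.

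| Assumed T (h) | r, to zero | THS | mCC | r, floor | THS | mCC |
|---|---|---|---|---|---|---|
| 3 | 0.177 | +126% | +466% | 0.334 | +20% | +200% |
| 4 | 0.273 | +47% | +267% | 0.411 | −3% | +143% |
| 5 | 0.354 | +13% | +183% | 0.477 | −16% | +110% |
| 6 | 0.420 | −5% | +138% | 0.531 | −25% | +88% |
| 8 | 0.522 | −23% | +92% | 0.613 | −35% | +63% |
| 10 | 0.595 | −33% | +68% | 0.672 | −40% | +49% |

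A true −60% shows as no change when r = 0.40. Decaying to zero, that is T = 7.5·ln 2/ln 2.5 = 5.67 h. With the floor, 2^(−7.5/T) = (0.40 − 0.190)/0.810 = 0.259, so T is about 3.8 h.

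**THS-versus-SA contrast.** For T of 3 to 6 h, the SA baseline is 0.50 to 0.84 of the THS baseline (to zero) or 0.78 to 0.90 (floor). The adjusted difference equals the raw difference minus slope × (mean SA baseline − mean THS baseline). The slope is positive and SA has the lower baseline, so the negative SA−THS difference moves toward zero.

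Size was checked by 3,000 simulated trials per setting at 80:40:40. Assumptions were median evening CO 20 ppm, log-scale SD 0.31 between subjects, 0.15 for each reading and 0.20 for half-life, first use at 06:30, and T of 4 to 6 h. The true SA−THS difference is −4.45 ppm.
- Three-arm model, decay to zero: −2.65 to −2.85 ppm (shrinkage 1 − 2.65/4.45 = 40% to 1 − 2.85/4.45 = 36%).
- Three-arm model, floor: −3.16 to −3.30 ppm (29% to 26%). By hand at T = 4 h: mean evening CO 20·exp(0.31²/2) = 20.98, times exp(0.15²/2) for reading error = 21.2. The baseline gap is 21.2 × (0.411 − 0.341) = 1.49 ppm, where 0.341 is midway between r at 9 h (0.361) and at 10.5 h (0.322). Times the fitted slope 0.88 this is 1.31, and −4.45 + 1.31 = −3.14.
- Model with THS and SA only, floor: −3.57 to −3.67 ppm (20% to 18%).

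**THS-versus-mCC contrast.** Both arms have the same pre-use baseline. With decay to zero, the simulated difference is 12.7 ppm under the SAP baseline and under a Day 0 evening baseline. The standard error rises from about 0.9 to about 1.0.

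**With a Day 0 evening baseline.** Simulated mean changes are about −59% (THS), +2% (mCC) and −81% (SA), against true values of −60%, 0% and −81%.

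**The case against.** The strongest reply is that the distortion is conditional and limited. Much of that stands.

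- A reader might infer that a real 60% reduction will appear as no change or as a rise. The documents do not support that. The half-life is assumed, the 0.40 ratio belongs to COHb, and the same COHb row implies that abstinent smokers do not reach zero. With that floor, a half-life of about 3.8 hours or less is needed.
- The SAP names the evening value for COHb but never says which of the four Day 5 CO tests is analysed. A Day 5 pre-use reading set against the Day 1 pre-use baseline would show −60% correctly.
- The tested secondary hypothesis is THS against mCC, and that contrast is unbiased. Raw CO levels are also summarised by arm.
- The SAP is not the only source of the morning trough. Under the protocol rule, a THS or mCC subject who starts at 06:30 also gets a reading from just before that time. Only the SA reading is a clear departure.
- COHb and nicotine also compare late-morning ambulatory values with evening baselines. What is particular to CO is a baseline timed differently by arm.
- The 10:00 AM rule was deliberate and suits the cough and withdrawal questionnaires, which are due by then.

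What the reply does not answer is the SA arm. Its CO baseline is taken during the intervention, and it enters a planned adjusted comparison.

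**Conclusion.** The point holds as a defect in one secondary endpoint. Followed as written, the plan gives SA a CO baseline taken after abstinence starts, outside the SAP's own baseline period and after the protocol's cut-off. The direction of the resulting THS-versus-SA bias follows from the schedule, provided THS subjects mostly start near 06:30; later starts narrow the gap between arms. The 18% to 40% shrinkage rests on the assumed half-life, CO level, floor and model.

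Percent change at non-morning readings is understated at every half-life examined (3 to 10 hours). The shorter ones can cancel or reverse the displayed reduction; the longer ones leave an attenuated reduction. The THS-versus-mCC contrast loses only a little precision. The primary endpoints and the stated power are untouched: in THS and mCC the COHb baseline is the Day 0 evening sample.

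**What to change.** In SAP Section 12.6.2.1:
1. Define the exhaled-CO baseline in all three arms as the Day 0 08:00-09:30 PM test, as is already done for nicotine and cotinine.
2. Name the Day 5 08:00-09:30 PM test as the CO value analysed, as is done for COHb.

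List the CO baseline in SAP Section 9. Note in the tables that CO at Days 30, 60 and 90 is a late-morning reading, so those percent changes still cross times of day.

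Keep the 10:00 AM rule for other SA variables. Restoring the 06:30 cut-off for all of them would move SA cough and withdrawal assessments made after 06:30 on Day 1 back to Day 0, while the other arms kept Day 1. It would also leave the trough in THS and mCC subjects who start at 06:30.

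The Day 0 evening CO test is already in the schedule, so the cost is SAP wording and the matching derivation.
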